6.3.4. Duration of Complete Response

DOCR is defined, for participants with a BOR of confirmed sCR or CR per IMWG criteria as determined by investigator, as the time from the first documentation of sCR or CR that is subsequently confirmed, until confirmed PD per IMWG criteria, or death due to any cause, whichever occurs first. The rules for PD confirmation are described in [Table 4](#).

DOCR will be calculated as follows:

$$\text{DOCR (months)} = [\text{date of event or censoring} - \text{first date of sCR or CR} + 1] / 30.4375$$

The censoring rules for DOCR are as described for PFS in [Section 6.3.5](#).

If at least 3 participants achieve a BOR of confirmed sCR or CR and subsequently have an event, DOCR will be estimated using the same Kaplan-Meier method as described for PFS in [Section 6.3.5](#) and displayed graphically where appropriate. Otherwise only listings will be provided.

The DOCR rate at 3, 6, 9, and 12 months (and in subsequent 6-month increments while there are participants still at risk) will be estimated with corresponding two-sided 95% CIs.

6.3.5. Progression-free Survival

PFS is defined as the time from the date of first dose until confirmed PD per IMWG criteria as determined by investigator or death due to any cause, whichever occurs first. The rules for PD confirmation are described in [Table 4](#).

PFS will be calculated as follows:

$$\text{PFS (months)} = [\text{date of event or censoring} - \text{date of first dose} + 1] / 30.4375.$$

PFS will be censored as follows:

- For participants who do not have an event (confirmed PD per IMWG criteria or death due to any cause), censoring will occur on the date of the last adequate disease assessment;
- For participants who start a new anticancer therapy (as defined in [Section 5.2.6](#)) prior to an event, censoring will occur on the date of the last adequate disease assessment before the new anticancer therapy;
- For participants with an event after a gap of 2 or more missing disease assessments, censoring will occur on the date of the last adequate disease assessment before the gap;
- Participants who do not have an adequate post-baseline disease assessment will be censored on the date of first dose of study intervention unless death occurs on or before the time of the second planned disease assessment (ie, ≤ 70 days after the date of first dose) in which case the death will be considered an event.

The censoring and event date options to be considered for the PFS analysis are presented in [Table 5](#). Adequate post-baseline disease assessment are defined in [Section 5.2.10](#), respectively.

Table 5. Outcome and Event Dates for PFS Analyses

Scenario	Date of Event/Censoring	Outcome
Progression or death 1. After at most 1 missing or inadequate post-baseline disease assessment or 2. ≤70 days after date of first dose of study intervention	Date of progression or death	Event
Progression or death after 2 or more missing or inadequate disease assessments ^a	Date of last adequate assessment ^a documenting no PD prior to new anticancer therapy or missed disease assessments	Censored
Neither progression nor death		
New anticancer therapy given prior to PD or death		

a. If there are no adequate post-baseline disease assessments prior to PD or death, then the time without adequate assessment should be measured from the date of first dose of study intervention; if the criteria were met, the censoring will be on the date of first dose of study intervention.

PFS = progression-free survival; PD = progressive disease

Kaplan-Meier estimates (product-limit estimates) will be presented and displayed graphically where appropriate, together with a summary of associated statistics including the median PFS time with 2-sided 95% CIs. The CIs for the median will be calculated according to Brookmeyer and Crowley, 1982.⁹

The PFS rate at 3, 6, 9, 12, 18, and 24 months (and in subsequent 12-month increments while there are participants still at risk) will be estimated with corresponding two-sided 95% CIs. The CIs for the survival function estimates at the timepoints defined above will be derived using the log(-log) method according to Kalbfleisch and Prentice¹⁰ (conftype=loglog default option in SAS Proc LIFETEST). The estimate of the standard error will be computed using Greenwood's formula. Frequency (number and percentage) of participants with each event type (PD or death) and censoring reasons will be presented along with the overall event and censor rates.

Reasons for censoring will be summarized according to the categories in [Table 6](#). If a participant meets multiple definitions for censoring the list will be used to define the hierarchy.

Table 6. PFS Censoring Reasons and Hierarchy

Hierarchy	Condition	Censoring Reason
1	Start of new anticancer therapy before event.	Start of new anticancer therapy
2	Event after 2 or more missing or inadequate post-baseline disease assessment after date of first dose	Event after missing or inadequate assessments ^a
3	No event and [withdrawal of consent date \geq date of first dose or End of study (EOS) = Participant refused further follow-up]	Withdrawal of consent
4	No event and lost to follow-up in any disposition page	Lost to follow-up
5	No event and [EOS present or disposition page for any EPOCH after screening says participant will not continue into any subsequent phase of the study] and no adequate post-baseline disease assessment	No adequate postbaseline disease assessment
6	No event and none of the conditions in the prior hierarchy are met	Ongoing without an event

a. More than 70 days after last adequate disease assessment.

The PFS time or censoring time and the reasons for censoring will also be presented in a data listing.

For the PFS analysis, sensitivity analyses will be performed, if $\geq 10\%$ of participants have died due to COVID-19 related reasons, these participants will be censored at the time of death.

6.3.6. Overall Survival

OS is defined as the time from the date of first dose until death due to any cause and will be calculated in months as follows:

$$\text{OS (months)} = [\text{date of death or censoring} - \text{date of first dose} + 1] / 30.4375$$

Survival status is expected to be collected irrespective of study intervention discontinuation or participant's request to discontinue study procedures. All participants who have not withdrawn consent for further participation in the study should be followed for survival until the end of the study. OS for participants not known to have died are censored on the date of last known alive.

OS time will be estimated using the same Kaplan-Meier method and displayed graphically as described for PFS in [Section 6.3.5](#). Median OS and 2-sided 95% CI will be provided. The OS rate at 12, 24, and 36 months (and in subsequent 12-month increments while there are participants still at risk) will be estimated with corresponding two-sided 95% CIs.

Frequency (number and percentage) of participants with death events and censoring reasons will be presented along with the overall event and censor rates. The event and censoring reasons are as follows:

- Death;
- Ongoing and no death;
- Withdrawal of consent;
- Lost to follow-up.

In addition, OS will be summarized with simple descriptive statistics (mean, standard deviation, minimum, median, and maximum) for duration of follow-up.

The OS time or censoring time and the reasons for censoring will also be presented in a listing.

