### 2.2. Background

#### 2.2.1. Multiple Myeloma

MM is a hematological B-cell malignancy characterized by dysregulated proliferation of BM plasma cells. Globally, there are approximately 176,000 new cases and 117,000 deaths per year attributed to MM.[4] The American Cancer Society estimates that for the US in 2021, approximately 34,920 new MM cases will be diagnosed and approximately 12,410 MM-related deaths will occur.[5]

Despite recent advances in treatment, MM remains an incurable disease and almost all patients, even those who initially respond to treatment, are expected to relapse. Even for patients who receive ASCT, the median time to relapse is only 17.2 months.[6] Similarly, for patients who are treated with novel PI-based or IMiD-based combination regimens as frontline treatment, the median time to relapse is 16.4 months.[7]

Moreover, MM patients typically cycle through many lines of treatment, having become relapsed/refractory to various therapeutic approaches. Trials that have treated patients with BCMA-directed therapy in the RRMM population have included heavily pretreated patients; for example, 57% of patients studied by Trudel et al had received  $\geq 5$  lines of therapy[8] and other trials have included populations receiving a median of 6 (range 3-18) prior therapies[9] and a median of 5 (range 3 to 18) prior therapies.[10]

Outcomes in the RRMM population are quite poor; for example, patients with RRMM who respond poorly to PI-based or IMiD-based regimens show a median OS of 13 months (95% CI: 11, 15).[11] Newer and more effective therapies have substantially increased patient benefit; however, in this real-world setting (N=3449), the most recent 4-year survival is only 75%.[12] Results from 2 trials in patient populations similar to the current protocol are summarized in Table 3. The lack of effective and durable therapeutic options highlights the unmet medical need in the RRMM patient population.

**Table 3. Efficacy Results for Available Therapies for Patients With Relapsed/Refractory Multiple Myeloma Who Have Received at Least 2 Prior Therapies**

Available Therapy	Prior Therapy for Eligibility	Median Number of Prior Therapies	ORR % (n/N)	mDOR (months)	Reference
Selinexor + dexamethasone	IMiD, PI, anti-CD38 mAb	8	25.3% (21/83)	3.8	XPOVIO® USPI
Belantamab mafodotin (belamaf) a	IMiD, PI, anti-CD38 mAb	7	32% (31/97)	11.0 months (95% CI, 4.2 months to not reached),	BLNREP USPI

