### **Overall Survival**

OS is defined as the time from the date of first dose until death due to any cause. Survival status is expected to be collected irrespective of study intervention discontinuation or

participant's request to discontinue study procedures. All participants who have not withdrawn consent for further participation in the study should be followed for survival until the end of the study. OS for participants not known to have died are censored on the date of last known alive.

OS will be summarized using Kaplan Meier method and displayed graphically. Median OS and 2-sided 95% CI will be provided.

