5. GENERAL METHODOLOGY AND CONVENTIONS

5.1. Hypotheses and Decision Rules

5.1.1. Hypotheses and Sample Size

5.1.1.1. Primary Endpoint

A Bayesian dual-criterion design⁶ will be used to estimate the primary endpoint of the true Grade ≥ 2 CRS rate during Cycle 1. With this design, the following criteria are defined:

- Bayesian statistical significance: Substantial evidence that the true Grade ≥ 2 CRS rate exceeds a pre-specified value. For this study, Bayesian statistical significance will be achieved if the posterior probability of the true Grade ≥ 2 CRS rate exceeding 35% is $<10\%$;
- Clinical relevance: The maximum number Grade ≥ 2 CRS events threshold that could justify further clinical development. For this study, it is defined as the median of the posterior distribution of the true Grade ≥ 2 CRS rate is $\leq 27\%$.

The analysis will use a Beta-binomial model (binomial sampling for number of Grade ≥ 2 CRS events and a beta prior distribution). A minimally informative beta prior distribution of the true Grade ≥ 2 CRS rate will be used. It is assumed a priori that the true mean Grade ≥ 2 CRS rate is 35%, so the prior distribution will be Beta (0.7, 1.3). Using this prior and based on the dual criteria defined above, approximately 76 participants will be enrolled and treated and a maximum of 20 participants with Grade ≥ 2 CRS events is allowed to meet the dual criteria in 76 participants. If exactly 20 participants in 76 participants experience Grade ≥ 2 CRS events, the observed Grade ≥ 2 CRS rate is 26.3% with median 26.3% and 90% credible interval of (18.7%, 35.0%) based on the posterior distribution.

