6. ANALYSES AND SUMMARIES

The primary analysis will be conducted once all enrolled participants have completed Cycle 1 or have otherwise discontinued the study intervention. At this analysis, the primary endpoint of Grade ≥ 2 CRS rate during Cycle 1 and the safety endpoints will be evaluated.

For primary completion date reporting purpose (initial CSR), the full scope of the statistical analysis including all the endpoints will be conducted once all participants have been followed for response for at least 6 months or have otherwise discontinued response assessments within the first 6 months of treatment.

The final analysis will be conducted once the last participant enrolled will have been followed for OS for at least 2 years.

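### SAP 6.3.6 summarizes OS time, which stops at death, as duration of follow-up; as a maturity measure this understates potential follow-up, and reverse Kaplan-Meier on the same data avoids that

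*SAP*

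**What the plan says.** SAP 6.3.6 computes OS in months from first dose to "date of death or censoring". It adds that "OS for participants not known to have died are censored on the date of last known alive". The main analysis is standard: "OS time will be estimated using the same Kaplan-Meier method and displayed graphically as described for PFS", with median OS, landmark rates, counts of deaths and of censoring reasons, and a listing.

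The same section then adds a second use of the OS variable: "OS will be summarized with simple descriptive statistics (mean, standard deviation, minimum, median, and maximum) for duration of follow-up". The summary is not restricted to survivors, and deaths are not treated as censored.

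Protocol 9.3.3.2 plans only Kaplan-Meier for OS and names no method for follow-up. Reverse Kaplan-Meier appears in neither document. On timing, SAP 6 states: "The final analysis will be conducted once the last participant enrolled will have been followed for OS for at least 2 years".

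**The concern.** A reader takes duration of follow-up as a statement about data maturity: how long participants were, or could have been, under observation for the endpoint. A statistic whose clock stops at death answers a different question. Someone who dies at month 3 has fully known survival, yet enters as 3 months of follow-up. The statistic therefore falls as mortality rises, even if every survivor has been observed for the whole planned period.

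At stake is interpretation only. At the final analysis the report could show a median follow-up of 18 months although the last participant enrolled had been followed for at least 24. A reader could then wrongly doubt the planned 24- and 36-month OS rates.

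**Working it through.** **Plan's own figure.** Neither document states an expected duration of follow-up, so there is nothing to reproduce.

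**Inputs from the documents.** OS time ends at death or censoring (SAP 6.3.6). About 76 participants are planned (SAP 5.1.1.1). The last participant enrolled has at least 24 months of OS follow-up at the final analysis (SAP 6). The initial CSR comes after at least 6 months of response follow-up (SAP 6). Protocol 2.2.1 gives a background median OS of 13 months in a poorly responding relapsed/refractory population; this is context, not a design assumption.

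**Assumed, because the documents are silent.** Uniform accrual over 12, 18 or 24 months; exponential OS with median m from 13 to 60 months; loss to follow-up of 0% or 5% by 24 months.

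**Step 1: large-sample value.** Let T be time to death and C potential follow-up. The SAP summarizes min(T, C), and

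P(min(T, C) > t) = 2^(−t/m) × P(C > t).

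The simple median is the t that makes this 0.5. Take C uniform on 24 to 36 months (12 months' accrual, true median 30):

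- For m ≤ 24, P(C > t) = 1 up to t = 24, so the median is exactly m: 18.0 for m = 18 and 24.0 for m = 24. The follow-up figure is then simply the median OS.
- For m = 36, t = 26.1 gives 2^(−26.1/36) × (36 − 26.1)/12 = 0.605 × 0.825 = 0.50. The simple median is 26.1.

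**Step 2: simulation at N = 76.** 1,500 trials per scenario, no loss to follow-up, final analysis. Entries are the average simple median; reverse Kaplan-Meier and the true median potential follow-up are given for comparison.

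| Median OS (months) | 12 months' accrual | 18 months' accrual | 24 months' accrual |
|---|---|---|---|
| 13 | 13.0 | 13.1 | 13.1 |
| 18 | 18.2 | 18.2 | 18.2 |
| 24 | 23.0 | 23.1 | 23.2 |
| 36 | 26.1 | 26.9 | 27.7 |
| 60 | 27.7 | 29.4 | 30.8 |
| Reverse Kaplan-Meier, all rows | 30.0–30.1 | 33.0–33.1 | 36.0–36.2 |
| True median potential follow-up | 30.0 | 33.0 | 36.0 |

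The gap to true potential follow-up is the last row minus the entry. Across the three accrual periods it runs from 17.0 to 22.9 months for median OS 13 (30.0 − 13.0; 36.0 − 13.1), 7.0 to 12.8 for 24, 3.9 to 8.3 for 36, and 2.3 to 5.2 for 60.

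The value near 23 at median OS 24 averages skewed sample medians; the large-sample value is 24.0 (step 1). It should not be read as falling systematically below the 24-month minimum.

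**Step 3: loss to follow-up.** With 5% loss by 24 months, reverse Kaplan-Meier gives about 29.6, 32.4–32.5 and 35.1–35.3 months for the three accrual periods, within 0.3 month of the true medians under the same loss.

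**Step 4: initial CSR.** Take C uniform on 6 to 18 months (true median 12). Solving 2^(−t/m) × (18 − t)/12 = 0.5 gives t = 9.4, 10.0 and 10.6 for m = 18, 24 and 36. For example, at m = 24: 2^(−10/24) × 8/12 = 0.749 × 0.667 = 0.50. The gaps are 12 − 9.4 = 2.6, 12 − 10.0 = 2.0 and 12 − 10.6 = 1.4 months.

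**The case against.** The strongest reply is that this is a choice of definition. Observed time from first dose to death or censoring is one recognised meaning of follow-up, and the SAP never says that it estimates potential follow-up. That stands: the statistic is not miscalculated, and it is low only against potential follow-up.

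Maturity can also be judged from other planned output: the Kaplan-Meier curve, landmark OS rates with CIs, censoring reasons, the listing of OS times, and the 2-year trigger for the final analysis. That stands too and limits the harm.

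Three stronger inferences are tempting, and the documents support none of them:

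- **That results or decisions are distorted.** No decision rule, sample size or estimate uses the summary. Nor do the documents say that it will accompany duration of response or PFS; SAP 6.3.6 mentions it once, under OS.
- **That reverse Kaplan-Meier would make the parts comparable.** Part 2 enrolment starts only after about 30 participants are in Part 1 (Protocol 4.1), so real follow-up differs between parts under any method. Reverse Kaplan-Meier largely removes the influence of mortality, not that difference.
- **That the descriptive statistics must go.** Keeping them under an accurate label is equally sound.

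Reverse Kaplan-Meier has limits of its own. It loses precision as deaths accumulate, which matters in a cohort as small as Part 2A Dose level 1 (8 planned in SAP 2.2; 12 treated according to Protocol 4.1). It also depends on last-known-alive dates, and off-treatment survival contact is only every 12 weeks.

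**Conclusion.** The point holds as a minor improvement. The direction is certain: every death before a participant's potential follow-up shortens that participant's recorded follow-up. The size is conditional on accrual, survival and losses, none of which the documents give. In the illustrations the understatement at the final analysis ranges from about 2 months (median OS 60, 12 months' accrual) to about 23 (median OS 13, 24 months' accrual). At an initial CSR with potential follow-up of 6 to 18 months it is about 1.4 to 2.6 months for median OS of 18 to 36. The Grade ≥2 cytokine release syndrome primary analysis and the Kaplan-Meier estimate of OS are untouched.

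**What to change.** Replace the sentence in SAP 6.3.6 with one stating that median duration of follow-up will be estimated by reverse Kaplan-Meier (OS times with the event indicator reversed, so that deaths are censored and censored participants count as events), with a 95% CI, overall and for the parts listed in SAP 5.2. If the descriptive statistics are kept, label them as observed time to death or censoring. Note that the estimate will be imprecise in very small cohorts, where a listing may serve better.

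The cost is one SAP sentence and a reversed indicator in a Kaplan-Meier analysis that is already planned. It needs no new data, no change in sample size and no error-rate adjustment.

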6.3.7. Time to Response

TTR is defined, for participants with an objective response per IMWG criteria as determined by investigator, as the time from the date of first dose to the first documentation of objective response that is subsequently confirmed. For participants with EMD at baseline, MR or better (for those with target plasmacytomas) and CR or better (for those with non-target non-bone EMD only) cannot be confirmed until a post-baseline EMD assessment is performed and the date of confirmed response cannot be prior to the initial EMD assessment date. TTR will be calculated in weeks as follows:

$$\text{TTR (weeks)} = (\text{date of first objective response} - \text{date of first dose} + 1) / 7$$

Time to VGPR (TTVGPR) and time to CR (TTCR) are defined similar to TTR but for participants with BOR of VGPR or better and sCR/CR, respectively.

TTR, TTVGPR, and TTCR will be summarized using simple descriptive statistics.

6.3.8. Minimal Residual Disease Negativity Rate

MRD negativity rate is defined as the proportion of participants with negative MRD (assessed by central lab) per IMWG sequencing criteria at any time from the date of first dose until the first documentation of confirmed PD, death or start of new anticancer therapy, whichever occurs first. The rules for PD confirmation are described in [Table 4](#).

MRD negativity will be defined by two thresholds, 10^{-5} and 10^{-6} .

The MRD negativity rate will be calculated along with the 2-sided 95% CI using the Clopper-Pearson method as follows:

- MRD negative with confirmed sCR/CR based on the Safety Analysis Set;

- CCI [REDACTED]
- [REDACTED]

Additional subgroups may be summarized if applicable.

6.4. Other Secondary Endpoints

6.4.1. Pharmacokinetic/Pharmacodynamics

Pharmacokinetic parameter analyses will be based on the PK Analysis Set. No PK parameter is reported.

A listing of elranatamab concentrations by study visit and timepoint will be generated.

Summary statistics will be provided for pre-dose and post-dose elranatamab concentrations at scheduled visits and nominal timepoints. Values below the limit of quantitation will be treated as zero in the descriptive statistics calculations. For additional details on handling missing and BLQ values, please refer to [Section 5.3.1](#). The summary table will include the number of participants, number of samples with BLQ values, mean, standard deviation, percent coefficient of variation (%CV), median, minimum, maximum, geometric mean, and geometric %CV. For this summary, samples that meet the following conditions will be included:

- For pre-dose samples, have the sample collected before the next dose administration.
- For the 24-hour and 48-hour post-dose samples, have the sample collected within $\pm 25\%$ of the nominal scheduled time.
- At least 2 consecutive planned doses were administered without interruption or reduction prior to trough sample collection.
 - Ex. C1D8 predose is included in the summary if C1D1 and C1D4 were administered as planned (ie, 4 and 20 mg, respectively);
 - Ex. C1D15 predose is included in the summary if C1D4 and C1D8 were administered as planned (ie, 20 and 76 mg, respectively).

Box and Whiskers plots of elranatamab trough concentrations after multiple doses for participants from the PK Analysis Set who meet the conditions stated above will be presented by study visit. The Box and Whiskers plots will be overlaid with geometric means.

In addition, the PK data from this study may be combined with PK data from other studies to develop a population PK model. The correlation between elranatamab exposure parameters and pharmacodynamic biomarker, efficacy and/or safety outcomes will be explored if data allow. Details of these modeling analyses are not within the scope of this SAP and will be described in a separate population PK and exposure response analysis plan.

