**Table 1. Schedule of Assessments: Part 1**

Visit Identifier	Screening	Treatment Period Cycle 1					Treatment Period (each 28 Day Cycle)		EOT/Visit	FU Visit	LTFU	Notes/Protocol Section
		Day 1	Day 4	Day 8	Day 15	Day 22	Cycles 2-6 Day 1	Cycle 7 Onwards Day 1				
Visit Window	Day-28 to Day-1		-1/+3 D	-1/+3 D	±3D	±3D	±3D	±3D	14 Dpost- final dose	28 to 35 days post- final dose	± 14D	
Phannacokinetics and Immunogenicity Assessments												
Blood sample for PK		X	X	X			X (C2, 4, 6)	X* (C10, 16, etc.)	X			Predose, 24, and 48 hrs postdose on C1D1. Predose and 24 hon C1D4. Collect predose on C1D8, and Day 1 of C2, 4, 6, then at D1 of eveiy sixth cycle starting from C10(ie, C10D1, C16D1, etc.). If CRS is suspected, additional PK samples should be collected if not ah-eady scheduled.  CCI
Blood sample for ADAs and Nabs		X					X (C2, 4, 6)	X (C10, 16, etc.)	X			Predose on C1D1, C2D1, C4D1, C6D1, and eve,y sixth cycle sta,tng C10(ie, C10D1, C16D1, etc). If AE possibly related to ADA occurs, additional samples for ADA and PK should be collected if not scheduled. See Section 8.7.

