**Table 2. Study Schedule of Assessments: Part 2**

Visit Identifier	Screening	Treatment Period Cycle 1					Treatment Period (each 28 Day cycle)			EOT Visit	FU Visit	LTFU	Notes/Protocol Section
		Day 1	Day 4	Day 8	Day 15	Day 22	Cycle2 Day1	Cycles 3-6 Day1	Cycle7 Onwards Day1				
Visit Window	Day-28 to Day-1		-1/+3 D	-1/+3 D	±3 D	±3 D	±3D	±3D	±3D	14D post- final dose	28 to35 days post-final dose	± 14D	
Phannacokinetics and Immunogenicity Assessments													
Blood sample for PK		X	X	X			X	X (C4 and C6)	X* (C8, 10, 13, etc.)	X			
Predose, 24 and 48 hrs postdose on C1D1. Predose and 24 hon C1D4 and C2D1. If no hospitalization required on C2D1 for Part 2B and Pait 2C, the 24 h postdose w-ill not be required.
 
Collect predose on C1D8 and on DI ofC2, 4, 6, 8, then at Day 1 of eve1y third cycle starting C10 (ie, C1OD1, C13D1, etc).
 
In the event of suspected CRS, unexpected or serious AE, or AE leading to discontinuation of study intervention, additional PK samples should be collected if not already scheduled.
 
CCI

Blood sample for ADAs and NAbs		X					X	X (C4 and C6)	C10, 16, etc	X			
Predose on C1D1, C2D1, C4D1, C6D1 and every sixth cycle sta1ting C10(ie, C1OD1, C16D1, etc). If AE possibly related to ADA occurs, additional samples for ADA and PK should be collected if not scheduled.
 
See Section 8.7.

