#### 4. STUDY DESIGN

##### 4.1. Overall Design

Study C1071009 is a prospective, open-label, multicenter, non-randomized Phase 1/2 study aimed to evaluate the safety (in particular the rate of Grade  $\geq 2$  CRS) of a priming dose regimen of eh-anatamab that involves premedication and 2 step-up priming doses to be administered within the first week of treatment (Part 1 and Part 2). Study C1071009 will include RRMM participants who are refractory to at least 1 PI, 1 IMiD, and 1 anti-CD38 mAb.

All participants enrolled in Part 1 and Part 2 will contribute to the primary objective of the study, ie, assessing the rate of Grade  $\geq 2$  CRS during C1, as the same dosing regimen is administered to all treatment groups during the first cycle.

Overall, at time of protocol amendment 4, Part 1 and Part 2 (Part 2A and Part 2B) were ongoing, and the enrollment is completed in all cohorts. Part 2C will not be explored. The RP2D was determined from Part 2A and is described below.

Twelve participants were enrolled and treated in Part 2A DL1 (116 mg Q2W from C2D1) and 7 were DLT evaluable. There was one DLT event. Eleven participants were enrolled and treated in Part 2A DL2 (152 mg Q2W from C2D1) and 7 were DLT evaluable. There was one DLT event. During the dose level review meeting (DLRM), the 152 mg Q2W dose was selected as the RP2D with a switch to 152 mg Q4W starting in Cycle 7 (for participants with an IMWG response of PR or better persisting for 2 months). In addition, participants in Part 1 dosed with 76 mg Q2W, with an IMWG response of PR or better persisting for 2 months were also permitted to switch to 152 mg Q4W. RP2D is currently investigated in Part 2B with a dosing of 152 mg Q2W or 152 mg Q4W (depending on IMWG response).

CCI  

All study parts are detailed below.

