### **9.3.3.3. Pharmacokinetic Analyses**

PK data analyses will include descriptive summary statistics of the predose and postdose serum concentrations of eh-anatamab by cohort, study visit and time point. In addition, the PK data from this study may be pooled with other studies to develop a population PK model. The correlation between eh-anatamab  $C_{max-24}$  after the first step-up dose (ie, 4 mg) and the probability of All Grade and Grade 2 and higher CRS will be evaluated; other relevant PK metrics may be explored. The results of these analyses correlating eh-anatamab exposure to probability of CRS will be reported in the clinical study report or a separate modeling report. The correlations between eh-anatamab exposure parameters and pharmacodynamic biomarker including cytokine data, efficacy and/or other safety outcomes will also be explored. The results of these modeling analyses may be reported separately from the clinical study report.

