5.2. General Methods

Unless otherwise specified, all efficacy analyses and safety analyses will be performed using the Safety Analysis Set. All analyses will be performed by part as follows:

- Part 1;
- Part 2;
 - Part 2A Dose level 1 (if Dose level 2 is identified as RP2D);
 - Part 2A (RP2D) + Part 2B;
 - CCI
- Part 1 and Part 2 Combined.

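### From Cycle 7 the planned PK tables and trough plots group predose samples by visit within part or cohort, not by the dose and interval in force, and admit the first post-switch sample unmarked

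*SAP*

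**What the plan says.** **Grouping.** SAP 6.4.1 states: "Summary statistics will be provided for pre-dose and post-dose elranatamab concentrations at scheduled visits and nominal timepoints". Trough box plots are by study visit. SAP 5.2 adds "All analyses will be performed by part as follows", listing Part 1, Part 2 (with Part 2A dose level 1 apart from Part 2A at the RP2D plus Part 2B; one sub-entry is redacted) and the two parts combined. Protocol 9.3.3.3 describes PK summaries "by cohort, study visit and time point". None of these names the dose and interval in use when the sample was drawn.

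**Eligibility.** A predose sample must precede the next dose, and "At least 2 consecutive planned doses were administered without interruption or reduction prior to trough sample collection". The SAP illustrates the condition with unequal doses: "Ex. C1D15 predose is included in the summary if C1D4 and C1D8 were administered as planned (ie, 20 and 76 mg, respectively". SAP 6.7.3.1 defines an interruption as a missed scheduled dose at the planned frequency, and a reduction as a non-zero dose below both the prior and the planned dose.

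**Regimens from Cycle 7.** Part 1 participants may be on 76 mg QW (not switched), 76 mg Q2W or the RP2D Q4W (SAP 2.2). Protocol 4.1 confirms that Part 1 participants responding on 76 mg Q2W "were also permitted to switch to 152 mg Q4W". In Part 2, a persisting PR or better moves a participant from Q2W to Q4W at Cycle 7 or later (protocol Table 2; SAP 6.7.3).

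**Predose sampling.** After Cycle 6, Part 1 samples at C10D1, C16D1 and so on (protocol Table 1). Part 2 samples at C8D1, C10D1, C13D1 and so on (protocol Table 2).

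**The concern.** PK is a secondary objective, and SAP 6.4.1 reports no PK parameters. Its visit tables and plots are therefore the only PK summaries the SAP plans; population PK is optional and left to a separate plan. Protocol 2.3.1 names disease progression from a lower trough in Part 2A, Part 2B and Part 1 from Cycle 7 as a risk of the longer intervals. A reader of the report will look to these tables for the trough on Q4W dosing.

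Two features obstruct that. Visit and part do not identify the regimen after Cycle 6, so one median or box can describe a mixture. And a participant's first sample after a switch still carries drug from the denser schedule, with nothing to mark it as transitional.

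**Working it through.** **Step 1: which regimens can share a cell?**
- Part 1, C10D1 onward: 76 mg QW, 76 mg Q2W, RP2D Q4W.
- Part 2, C8D1 onward, within either dose-level group: Q2W and Q4W at the same dose.
- The overall Part 2 and combined columns mix dose levels as well.

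**Step 2: does the filter catch a switch?** Take a Part 2 participant on 152 mg who switches at C7D1. The two doses before the C8D1 predose sample are C6D15 (152 mg, Q2W schedule) and C7D1 (152 mg, first Q4W dose). Both are planned and given. No scheduled dose is missed, and neither dose is below the prior or planned one. The sample passes after a single 28-day interval.

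For a Part 1 participant switching at C7D1, C10D1 follows C7D1, C8D1 and C9D1, which is three Q4W intervals. A Part 1 switch at C9D1 gives one.

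**Step 3: how large is the carry-over?** The documents give no half-life. I assume linear one-compartment kinetics, instantaneous input, steady Q2W dosing before the switch, and a half-life of 15 to 30 days. As a cross-check, protocol 2.3.1 predicts that the 152 mg Q2W trough is about 14% (free) or 10% (total) below 76 mg QW. With x = exp(-7k), that ratio is 2x/(1+x):
- 0.86 gives x = 0.86/1.14 = 0.754, half-life 7·ln2/(-ln x) = 17.2 days.
- 0.90 gives x = 0.90/1.10 = 0.818, half-life 24.2 days.

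Both lie inside the assumed range.

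Let y = exp(-14k), the fraction remaining after 14 days. At the same dose, in units of dose:
- steady Q2W trough = y/(1-y)
- steady Q4W trough = y²/(1-y²)
- first Q4W trough after steady Q2W = y × y/(1-y), which is (1+y) times the steady Q4W trough
- excess over the steady Q4W trough after n Q4W intervals = y^(2n-1)
- steady Q2W trough : Q4W trough = 1/y at C8D1 and (1+1/y)/(1+y⁵) at C10D1, for a switch at C7D1

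| Half-life (days) | 15 | 17.2 | 24.2 | 30 |
|---|---|---|---|---|
| y | 0.524 | 0.569 | 0.669 | 0.724 |
| First Q4W trough / steady Q4W trough (C8D1) | 1.52 | 1.57 | 1.67 | 1.72 |
| Excess after two Q4W intervals | 14% | 18% | 30% | 38% |
| Excess after three (C10D1) | 4% | 6% | 13% | 20% |
| Q2W : Q4W trough at C8D1 | 1.91 | 1.76 | 1.49 | 1.38 |
| Q2W : Q4W trough at C10D1 | 2.80 | 2.60 | 2.20 | 1.99 |

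Superposition over the actual Part 2 dose calendar, including Cycle 1, gives 1.57 to 1.66 at C8D1 for half-lives of 17.2 to 24.2 days, so the steady-state approximation is adequate.

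**Step 4: Part 1 at C10D1.** Superposition over the Part 1 calendar, with the switch at C7D1, gives 76 mg QW : 76 mg Q2W : 152 mg Q4W of 2.98 : 1.34 : 1 at 17.2 days and 2.39 : 1.19 : 1 at 24.2 days. The Q4W sample exceeds its steady-state value by 7% to 16%. If Q4W starts at C9D1, the excess is 18% to 25%.

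**The case against.** The strongest defence is that these are descriptive tables and the rule is a dosing-compliance filter: its own examples accept rising doses, and the SAP never claims steady state. A listing of every concentration is planned, and population PK could handle changing regimens. The quantified trough prediction in protocol 2.3.1, for 152 mg Q2W from Cycle 2, can be assessed at C4D1 and C6D1, before any interval switch. The post-Cycle 7 PK rows in the schedules also carry redacted notes, so some regimen-specific sampling may be hidden. All of this stands, and it limits the importance of the point. It does not remove it: the text of SAP 6.4.1 is unredacted and has no regimen grouping, and a listing is not a summary.

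Three stronger readings are tempting and should not be drawn.
- **The SAP reports an inflated Q4W trough.** A reader might infer this, but the SAP has no Q4W stratum; the carry-over sample enters an unlabelled visit cell.
- **The longer interval is made to look better covered.** This does not follow. Participants left on QW or Q2W are those without a persisting response, and the protocol describes soluble BCMA as a sink for unbound drug. Regimen is therefore confounded with disease burden, and the direction of the net bias is not known, least of all for free drug.
- **The Part 2 C2D1 24-hour sample has the same fault.** The documents require two 76 mg doses before escalation but do not say what is given on C2D1 to those who lack them.

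**Conclusion.** The point holds as a defect of presentation in a secondary, descriptive analysis. The mixing and the unmarked transition sample follow from the text alone. The sizes rest on the assumed kinetics.

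Carry-over is mainly a Part 2 C8D1 matter for participants who switch at Cycle 7. By C10D1 it is small for that group, though larger for later switchers. The mixing persists at every later visit. The QW to Q4W contrast in Part 1 is the extreme pair; 76 mg Q2W and 152 mg Q4W differ by only about 1.2 to 1.3 fold at half-lives of 17 to 24 days. How many participants will be on each regimen at a given visit cannot be told from the documents.

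**What to change.** In SAP 6.4.1, for predose samples from Cycle 7 onward only:
- Summarise and plot by dose and interval in force at sampling, within each part: 76 mg QW, 76 mg Q2W and RP2D Q4W in Part 1; 116 or 152 mg Q2W and Q4W in Part 2; and any later interval the protocol allows.
- Label each dose with the interval planned to run from it, and require the two preceding planned doses to share dose and interval.
- Show samples that fail this, such as C8D1 after a C7D1 switch, in a separate transition row.
- Do not call the retained samples steady state. After two Q4W intervals the model above still leaves an excess of 14% to 38%.

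Leave the rule and its examples unchanged for Cycles 1 to 6. A same-dose condition there would discard every C1D8 predose sample, which follows 4 mg and 20 mg by design and which the SAP expressly includes.

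The cost is a wording change and one derived variable from dosing records already collected; no new samples. Some regimen-by-visit cells will be small, and under SAP 5.3.1 those with fewer than three values show only minimum and maximum. The SAP is based on Amendment 2 and the protocol is now at Amendment 4, so an SAP update could carry the change.
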